Other mobility measures will also be examined as secondary outcomes in models otherwise identical to those in a, b, and c. The analyses will be repeated for cognition, with the speed obtained on Trailmaking B at T_{36} as the primary outcome and other cognitive measures as secondary outcomes. Additional secondary analyses will use logistic and ordinal models with the same predictors and incontinence presence and severity, respectively as outcomes; the progression model (c) will be fit as binary or ordinal generalized linear mixed models.

Hypothesis 4: Reduced total WMH and decreased markers of tissue damage on DTI at T_0 and at T_{36} are linked to better mobility at T_{36} . (Paths B+E)

The same outcomes will be used for this hypothesis as in hypothesis 1, with identical analyses except that WMH, and DTI indices (FA and MD) as continuous variables will be the primary predictor of interest. The power for this hypothesis as expressed as increased in explained variability (R^2) will be the same as for hypothesis 1: 85% power to achieve an increase in R^2 of 0.0533; we actually observed an increase in R^2 of 0.1658, to 0.2925, as the effect of tWMH, corresponding to a reduction in gait

velocity of 0.0063 m./sec. for each 0.1% increase in tWMH. The analyses will be repeated for gait velocity at T₁₈ with a model corresponding to analysis b, and for the following progression model replacing the model for analysis c:

$$Y_{i0} = b_{i0} + \beta_C (X_{i0}) + \text{cross sectional covariates} + \text{residual error}$$

$$Y_{i18} = b_{i0} + \beta_C (X_{i0}) + \beta_L (X_{i18} - X_{i0}) + \text{cross sectional covariates} + \text{longitudinal covariates} + \text{residual error}$$

$$Y_{i36} = b_{i0} + \beta_C (X_{i0}) + \beta_L (X_{i36} - X_{i0}) + \text{cross sectional covariates} + \text{longitudinal covariates} + \text{residual error}$$

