Here, Y_{i0} , Y_{i18} , and Y_{i36} are the outcomes (mobility or imaging) at T₀, T₁₈ and T₃₆ for study participant i , X_{i0} , X_{i18} , and X_{i36} the tWMH at T₀, T₁₈ and T₃₆ for study participant i , and b_{i0} is a random intercept that is used to take into account the fact that repeated measurements on individuals are not independent. The model will be fit as a linear mixed model³⁷. Again the other β_j 's are fixed effects although we will consider the possibility that treating them as random effects will add to the model fit. The parameters of interest are β_C and β_L , the cross-sectional and longitudinal effects of the imaging measures on mobility over the 36-month follow-up. As secondary analyses we will consider interactions with treatment group and nonlinear effects in time. Analyses will be repeated for the other mobility and cognitive measures, also as linear mixed models, and urinary incontinence presence/severity as binary and ordinal generalized linear mixed models.

Hypothesis 5: Total WMH at T₀ and at T₃₆ mediate the effect of treatment group, showing that

the mechanism by which reduced ABP is linked to better mobility occurs by reducing total WMH.(Paths C - A&B) Mediation models allow the evaluation of hypotheses using biological mechanisms. In this case, we believe that much of the salutary effect of reduced ABP results from reduced WMH. Assessing mediation involves estimating direct effects (Path C, above) and indirect effects (Paths A and B, above) in multistage predictor models by adding potential mediators to models describing the effect of a predictor on the outcome. To the extent by which WMH mediates the effect of BP, the effect of BP will be reduced in the model that includes WMH compared to the model not including WMH. We saw this in our observational study, as the adjusted effect of SBP in the pseudo-treatment group was reduced

from a .15 m/sec. to a .1 m/sec. difference in gait velocity when WMH was added as a model predictor.

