Product of coefficients methods^{35,36} will be used for formal statistical inference regarding the mediation. Specifically, we will estimate the product of the effect estimated for hypothesis 2 corresponding to Path A (the effect of intervention group on total WMH at T₃₆), and the effect estimated for hypothesis 3 corresponding to Path B (the effect of WMH at T₃₆ on gait velocity at T₃₆). The magnitude of this product turns out to be proportional to the change in the effect of intervention group on gait velocity at T₃₆ when WMH at T₃₆ is added to a regression model of gait velocity at T₃₆ as a function of intervention group. Similar models will be used to assess outcomes at T₁₈, and the cognitive outcomes. As formal tests for mediation using the product of coefficients method require larger sample sizes than available in this study, we will treat results from analyses in Hypothesis 5 as preliminary, to be potentially verified by a larger study should the main effects in Hypotheses 1-3 be confirmed.

Hypothesis 6: Diffusion tensor imaging (DTI) indices (FA, MD) at T₀ and at T₃₆ mediate the effect of treatment group, showing that the mechanism by which reduced ABP is linked to better mobility occurs by preserving brain WM microstructural integrity (FA, MD).

(Paths C – D&E) The same analysis as used for hypothesis 5, except that the mediating effect of the DTI indices will be assessed.

Missing Data.

Death and study attrition are associated with age-related diseases. Failure to account for this informative censoring may result in biased estimates of dementia risk and cognitive decline.³⁷ Hence, we will collect data by telephone to assess the degree to which living participants who fail to appear for their final assessment differ from participants who complete the study. As mentioned above, we will use telephone administration of a validated mobility assessment³⁹ and the method developed by [name] and colleague³⁰ to estimate mobility outcomes through multiple imputation or joint modeling that would have been

observed had the participants appeared for their clinical assessment. While our primary efficacy outcome analysis will be limited to participants who complete the study, this will be the first trial in aging with the potential to assess the impact of informative dropout beyond usual sensitivity analyses.

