8.3 Sample Size and Randomization

We conservatively estimate that at least 140 of the original 200 participants will complete assessments at 35 months. We analyzed a subset of participants in our earlier observational study in order to mimic the results of the two treatment groups we expect to see in the intervention study. For a standard care arm, we selected participants in the observational study who had 24 hour systolic BP between 140 and 150 mmHg, inclusive, at follow-up, and for the intensive treatment arm, we selected participants with 24 hour Systolic BP between 120 and 130 mmHg, inclusive, at follow-up. A regression of gait velocity over 8 feet on our covariates age, sex, and 24 hour systolic BP at baseline showed an r^2 of 0.1267. If we see similar results in the intervention study, 140 participants (70 in each group) will give us 85% power to observe an increase in r^2 of 0.0533 to 0.1800. In our prior observational study, we saw an increase in r^2 of 0.1082 to 0.2349, with a difference in gait speed between the two simulated treatment groups of 0.15m./sec. While the 0.15m/sec gait speed difference between the low and high BP groups appears small, it represents only 2 years of observation. Mobility impairment linked to WMH is a long-term decremental process that limits gait velocity over 10 or more years. Thus a “small” 2-year differential is both believable and meaningful. We are therefore confident that the proposed study has ample power to find smaller yet clinically significant effects for our primary outcome. A regression of total WMH on covariates age, sex, and 24 hour systolic BP at baseline showed an r^2 of 0.1162. Similar results in the intervention study imply 85% power to observe an increase in r^2 of 0.0540 for the effect of the treatment arm, to 0.1702. We actually observed an increase of 0.0861, to 0.2023, in the prior observational study, corresponding to a difference between the two simulated treatment groups of 0.93% total WMH.

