For mobility, cognition, and depression, variables are defined as in (1) with the following additions: δ_i is residual error in the model for change in WMH, and m_{i1} and m_{i2} are the values of WMH at baseline and follow-up, respectively. Some mediation measures of interest are as follows:

$$CDE = \beta_T$$

$$INT_{REF} = \theta_{INT} \alpha_0$$

$$INT_{MED} = \theta_{INT} \alpha_1$$

$$PIE = \theta_M \alpha_1$$

The controlled direct effect $CDE = \beta_T$ is the effect of treatment assignment in the absence of any WMH, $INT_{REF} = \theta_{INT} \alpha_0$ is the reference interaction between treatment assignment and WMH, $INT_{MED} = \theta_{INT} \alpha_1$ is the mediated interaction, and $PIE = \theta_M \alpha_1 x_i$ is the pure indirect effect. Combinations of these derived measures will be used to assess the degree of mediation, as described in VanderWeele. T.J. (2015). Explanation in Causal Inference: Methods for Mediation and Interaction, Oxford University Press. In particular, the proportion mediated is $\frac{INT_{REF} + INT_{MED} + PIE}{CDE + INT_{REF} + INT_{MED} + PIE}$.

Bootstrap standard errors and confidence intervals will be used for statistical inference, including estimation of standard errors and confidence intervals.

In secondary analyses, age, sex, and resultant ambulatory systolic BP at 36 months regardless of treatment assignment will be considered as mediators through similar methods. Specifically, age, sex, and systolic BP will replace $m_{i2} - m_{i1}$ in the model above and similar measures of interaction and mediation will be estimated.

7. Special Interest adverse events (falls, nervous system and vascular disorders) as related to numerous predictors of interest.

These outcomes are all count variables, so we use Poisson regression with each of the following predictors.

$$\log(\mu_i) = \log(n_i) + \beta_0 + \beta_1 x_i$$

Here μ_i is the count, n_i is the number of months in study, β_0 is the intercept with $\exp(\beta_0)$ interpreted as the rate of AE with mobility scale is zero, x_i is the predictor of interest, mobility scale and β_1 is the log rate ratio between groups and $\exp(\beta_1)$ is interpreted as the estimated ratio of rates for two subjects differing by one in their predictors of interest scale. This analysis will be repeated for the following predictors described below:

- a. Mobility variables
- b. Cognitive variables
- c. Treatment assignment
- d. Blood pressure
- e. Age
- f. Gender

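### The SAP's proportion mediated counts the reference interaction as mediation, and age and sex are listed as mediators of a randomised treatment

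*SAP*

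**What the plan says.** SAP item 6 models the change in WMH as α_0 + α_1x, where x is treatment. It models the 36-month outcome with a treatment term β_T, a WMH-change term θ_M and a treatment-by-WMH-change term θ_INT. From these it defines four components:

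- CDE = β_T
- INT_REF = θ_INT × α_0
- INT_MED = θ_INT × α_1
- PIE = θ_M × α_1

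It then picks out one summary. "In particular, the proportion mediated is" introduces the fraction "INT_{REF} + INT_{MED} + PIE}{CDE + INT_{REF} + INT_{MED} + PIE", whose first group is the numerator and second the denominator. The CDE, it says, "is the effect of treatment assignment in the absence of any WMH".

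For secondary analyses it adds that "age, sex, and resultant ambulatory systolic BP at 36 months regardless of treatment assignment will be considered as mediators", each replacing the WMH-change term in the same model.

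Protocol section 8.2, Hypothesis 5, uses a product-of-coefficients method for the same question. It also says "we will treat results from analyses in Hypothesis 5 as preliminary", because the sample is too small for formal tests.

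**The concern.** An effect is mediated by WMH only if treatment changes WMH and that change alters the outcome. The first link is α_1, and INT_REF does not contain it. INT_REF describes how far the treatment effect differs with WMH change, evaluated at the reference arm's average change. That is effect modification.

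Age and sex are fixed before randomisation, so for them α_1 is zero apart from chance imbalance. There is nothing for them to mediate.

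Three of the secondary objectives in protocol section 1.2 ask whether WMH accrual mediates the changes in mobility, cognition and urinary function, and this is the only summary ratio the SAP specifies for that question. A ratio that can be positive without mediation, or near zero with it, could mislead readers about mechanism.

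**Working it through.** The SAP gives no numerical value for this ratio, so there is no figure to reproduce. The check is algebra on its own equations, followed by illustrations.

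**1. Algebra.** The treatment effect on change is β_T + θ_INTα_0 + θ_INTα_1 + θ_Mα_1, which is the sum of the four components, so the denominator is right. The part that passes through treatment's effect on WMH is (θ_M + θ_INT)α_1 = INT_MED + PIE. The SAP numerator adds θ_INTα_0. With α_1 = 0 the SAP ratio becomes

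θ_INTα_0 / (β_T + θ_INTα_0),

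which is zero only if θ_INT or α_0 is zero. The protocol expects WMH to accrue over 36 months, so α_0 = 0 is unlikely. The protocol's product of coefficients is zero when α_1 = 0, so the two documents can disagree on the same data. If θ_INT = 0, both ratios have the same target.

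A simulated data set of 2,000,000 (α_1 = 0, α_0 = 0.5, θ_INT = 0.05, β_T = 0.05) gave 33.8% by the SAP formula and 0.0% without INT_REF. The four components summed to the observed difference of 0.0754 m/s.

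**2. Inputs for the illustrations.**
- β_T = 0.10 m/s, borrowed from Hypothesis 5, where the prior cohort's effect fell "from a .15 m/sec. to a .1 m/sec. difference in gait velocity when WMH was added as a model predictor".
- θ_M = −0.063 m/s per 1% WMH, from Hypothesis 4, which reports a reduction in gait "velocity of 0.0063 m./sec. for each 0.1% increase in tWMH" (0.0063 × 10).
- α_0, α_1 and θ_INT are assumed; the documents do not give them.

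**3. No effect on WMH (α_1 = 0).** The true mediated share is 0% in every cell. The SAP ratio is:

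| θ_INT (m/s per 1%) | α_0 = 0.3% | α_0 = 1.0% |
|---|---|---|
| 0.015 | 0.0045/0.1045 = 4.3% | 0.015/0.115 = 13.0% |
| 0.03 | 0.009/0.109 = 8.3% | 0.03/0.13 = 23.1% |
| 0.06 | 0.018/0.118 = 15.3% | 0.06/0.16 = 37.5% |
| −0.03 | −0.009/0.091 = −9.9% | −0.03/0.07 = −42.9% |

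The value 0.06 is extreme, about the whole WMH slope. Values of 0.015 to 0.03 are a quarter to a half of it.

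**4. Real mediation (α_0 = 1.0%, α_1 = −0.3%).** PIE = −0.063 × −0.3 = 0.0189.
- θ_INT = +0.03: INT_REF = 0.03, INT_MED = −0.009, total = 0.1399. The SAP ratio is 0.0399/0.1399 = 28.5%; without INT_REF it is 0.0099/0.1399 = 7.1%.
- θ_INT = −0.03: INT_REF = −0.03, INT_MED = 0.009, total = 0.0979. The SAP ratio is −0.0021/0.0979 = −2.1%; without INT_REF it is 0.0279/0.0979 = 28.5%.

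**5. Noise when there is neither mediation nor interaction.** Protocol section 8.3 reports "we saw an increase in r^2 of 0.1082 to 0.2349" with a 0.15 m/s difference. For equal groups and treatment uncorrelated with the covariates, Var(Y) = 0.25 × 0.15²/0.1082, so SD(Y) = 0.228. The residual SD is 0.228 × √(1 − 0.2349) = 0.199. The simulation used 20,000 trials of 70 per arm, WMH change with mean and SD 0.5 (assumed), and no baseline outcome in the model. The 95% range of the SAP ratio was about −95% to +91% at a total effect of 0.10 m/s, and −52% to +52% at 0.15. Without INT_REF it was −21% to +17% and −11% to +10%. This is imprecision, not bias.

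**6. Age and sex.** With α_1 = 0 the SAP ratio is θ_INT × mean(m)/total, where m is the variable placed in the mediator slot.
- Age, with mean 82 (the prior cohort's), total 0.10 and θ_INT = 0.001 per year (both assumed): in years, 0.082/0.10 = 82%; as years above 75, 0.007/0.10 = 7%; centred at 82, 0%.
- Sex, half of each (assumed), total 0.15 and θ_INT = 0.05 (assumed): coded 0/1, 0.025/0.15 = 17%; coded 1/2, 0.075/0.15 = 50%.

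Shifting the origin of m changes β_T and α_0 but not θ_M, θ_INT or α_1. The ratio without INT_REF is therefore unaffected by coding origin.

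**The case against.** The strongest reply is that the error is one of labelling. The SAP ratio equals (total − CDE)/total, the share of the treatment effect that would disappear if WMH change were held at zero. That is a legitimate quantity. It resembles Hypothesis 5, which judges mediation by how far the treatment effect shrinks once WMH is in the model. This stands as far as it goes, and renaming the ratio is an acceptable repair. But Hypothesis 5 has no interaction term, and there the shrinkage is the product of coefficients. Once θ_INT is added, the two quantities part.

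Other points carry some weight:

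- The four components are already planned with bootstrap intervals, so a reader could rebuild another ratio. A wrongly named summary would still be reported.
- The SAP already stratifies by median age and gender, so effect modification is partly covered. That does not make age or sex a mediator. The SAP promises similar measures for them without expressly naming a proportion mediated, though that is the natural reading.
- The 0.063 slope is for WMH level rather than change, and 0.10 m/s comes from observational groups without an interaction term. The sizes are illustrations, not forecasts.
- The noise range is too wide for the SAP's joint model, which also uses the baseline outcome. With an assumed baseline correlation of 0.7, it narrows to roughly −60% to +57% at a total effect of 0.10.
- Item 6 covers urinary function through its item 3, but its explicit definitions are for mobility, cognition and depression. How the ratio carries over to the ordinal model is not spelled out.

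**Conclusion.** The concern holds. As written, the ratio is not a proportion mediated: it can be non-zero with no effect of treatment on WMH, and it can conceal an effect that is there. The error needs a non-zero interaction and a non-zero mean WMH change in the reference arm; without interaction there is only a loss of precision. For interactions of a quarter to a half of the protocol's WMH slope, the false share is 4% to 23% under the assumed 0.3 to 1.0% reference-arm change.

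Listing age and sex as mediators is a separate error and does not depend on any assumed value.

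A smaller wording error is that the mediator is WMH change, so β_T is the effect at zero change. It cannot describe patients without WMH, because entry requires at least 0.5%.

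This should be corrected, but it bears on secondary analyses that the protocol itself treats as preliminary. The primary efficacy analysis and the sample size are not affected.

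**What to change.** In SAP item 6:

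1. Define the proportion mediated as (INT_MED + PIE)/(CDE + INT_REF + INT_MED + PIE). Alternatively, keep the present ratio and name it the share of the effect not due to the CDE.
2. Report the four components, with their bootstrap intervals, beside whichever ratio is used.
3. Remove age and sex from the mediator list and fit treatment-by-age and treatment-by-sex terms. Achieved 36-month systolic BP may stay as a mediator, since treatment acts on it.
4. Describe the CDE as the effect at zero WMH change.

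Optionally, add the protocol's covariates (age, sex, baseline 24-hour systolic BP) to the mediator and outcome models. The baseline outcome should not be added as a covariate, because it is already a response in the joint model.

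The cost is SAP wording and a few lines of code, with no new data and no change to the primary analysis.

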5.6 Description of Evaluations

Resting clinic BP: Taken on a semi-automated digital device (Suntech TM2420, Morrisville, NC) with an appropriate cuff. After sitting 5 min, BP will be taken twice, 2-3 minutes apart in the non-dominant arm and averaged. BP readings will be taken between 8 and 11 am, before taking antihypertensive medication.

24-hour ambulatory BP Monitoring (ABPM): conducted after antihypertensive washout and prior to initiation of investigative therapy using the Oscar II BP device (Suntech Medical Instruments, Morrisville, NC) which has been validated independently.¹⁸ The device is a light, comfortable automated BP recorder. Eighty BP

readings will be programmed during the 24-h study. Monitors will measure BP and heart rate every 15 min from 6 am to 10 pm, and every 30 min from 10 pm to 6 am.^{19, 20.}

Follow-up ambulatory BP recordings will be made at 3 months to evaluate response to therapy and at 6 months if medications were adjusted at 3 months to ascertain if systolic BP goals were achieved. Data will be transferred to Accuwin software program (Suntech Medical Instruments, Morrisville, NC) for analysis. Components of the ABPM for analysis will include the 24-hour mean systolic and diastolic BP, the awake and sleep BPs, and the early morning BP (the difference between the 2 hour post-awakening BP – the 2 hour pre-awakening BP) as previously described.^{20, 21.}

A baseline electrocardiogram (ECG): a standard 12-lead ECG will be obtained at baseline, 18 months and end of study – these will be assessed by study physicians [name] and/or [name].

Laboratory tests (safety): CBC, glucose, BUN, creatinine, liver enzymes and urinalysis, sodium and potassium. Abnormal results will require further testing or referral for treatment before (or in lieu of) study participation.

Laboratory tests (research): lipid profile (Total, HDL and LDL cholesterol, and triglycerides).

Mobility Measures: Performance will be assessed primarily by timing.

- walking-moving
- Gait Speed: Gait speed will be measured as participants walk at a comfortable pace over an 8-meter course with 1 meter for acceleration and deceleration.
- Stair Ascent/Descent: stair ascent and descent will be used as a measure of walking-moving. We have previously shown stair descent time to be predicted by WMH²². Ascent and descent of 4 steps at a comfortable pace will be timed separately.

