- Ambulatory blood pressure monitoring if clinic systolic BP has been stable for visits 2 and 3 according to treatment assignment. If not, patients will return in 2-4 weeks for re-assessment of BP stability. Antihypertensive drug titration will be based on ambulatory BP from this point forward.
- Dispense medications for next 3 months

Visit 4 (6 months post-randomization) – Patients will return for evaluation of antihypertensive response to therapy according to randomized treatment group. Procedures previously defined above will be done at this visit:

- Medical history, concomitant medications, adverse events, medication compliance
- Standardized clinic BP measurements, body weight and height
- Antihypertensive medication titration or down-titration as appropriate – ad hoc ambulatory BP can be performed here to address therapeutic goals and if deemed medically necessary.
- Safety laboratory studies (potassium, creatinine, BUN) if clinically necessary

- Electrocardiogram if clinically necessary
- Dispense medications for next 6 months

Visit 5 (12 months post-randomization) – Patients will return for evaluation of antihypertensive response to therapy according to randomized treatment group. Procedures previously defined above will be done at this visit:

- Medical history, concomitant medications, adverse events, medication compliance
- Standardized clinic BP measurements, body weight and height
- Antihypertensive medication titration or down-titration as appropriate; ad hoc ambulatory BP can be performed here to address therapeutic goals and if deemed medically necessary.
- Laboratory studies (potassium, creatinine, BUN, glucose, ALT, cholesterol profile)
- Electrocardiogram if clinically necessary
- Home BP monitoring
- Dispense medications for next 6 months

Visit 6 (18 months post-randomization) – Patients will return for evaluation of antihypertensive response to therapy according to randomized treatment group and will have comprehensive testing for WMH, mobility, cognitive function as well as blood pressure control. Procedures previously defined above will be done at this visit:

- Medical history, concomitant medications, adverse events, medication compliance
- Standardized clinic BP measurements, body weight and height
- Antihypertensive medication titration or down-titration as appropriate; ambulatory BP will be performed to evaluate achievement of therapeutic goals according to randomized treatment strategy.

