5.6.4 Completion/Final Evaluation

Visit 9 (36 months post-randomization) - Patients will return for evaluation of antihypertensive response to therapy according to randomized treatment group and will have final research testing for WMH, mobility, cognitive function as well as blood pressure control. Procedures previously defined above will be done at this visit:

- Medical history, concomitant medications, adverse events, medication compliance
- Standardized clinic BP measurements, body weight and height
- Antihypertensive medication will be prescribed/continued according to clinical goals for long-term management. Clinical follow-up will be arranged with either primary care physician, one of the study physicians, or both, depending on wishes of study patient.
- Safety laboratory studies (potassium, creatinine, BUN) if clinically necessary
- Electrocardiogram
- Ambulatory blood pressure monitoring
- MRI acquired at UCONN neuroradiology
- Mobility Testing
- Cognitive Testing
- Questionnaires related to urinary function, QOL

- Home BP monitoring

Early termination patients who complete at least 18 months of randomized therapy will be considered completed study patients and all comprehensive tests will be completed that were designated for visit 9.

SAFETY ASSESSMENTS

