6. INTERVENTION DISCONTINUATION

- A. Patients will be discontinued from their antihypertensive intervention if it is deemed that the treatment(s) or blood pressure level is no longer safe or appropriate based on clinical condition (e.g. development of congestive heart failure that mandates a specific regimen or development of a terminal malignancy).
- B. Potential reasons for discontinuation of the intensive treatment might include untoward symptoms associated with low blood pressure related to development of a new morbidity (e.g. blood loss, sepsis) or intolerance to therapy (e.g. lightheadedness/syncope. In rare cases, hyperkalemia or hyponatremia may develop that would be unmanageable under the constraints of the protocol-drive therapies. Hypokalemia will be managed with aggressive potassium replacement to maintain serum levels > 3.5 meq/L.
- C. As this is an intention-to-treat trial, patients who discontinue treatment interventions will be invited to participate in clinical follow-up and all comprehensive outcome studies at months 18 and 36 of the trial.
- D. In the event of temporary discontinuation of antihypertensive treatment (e.g. need to withhold antihypertensive medications due to surgery, post-operative bleeding, infection or other causes of low blood pressure), reassessment of these individual patients will be made

in the research clinic for a return of BP levels towards baseline, and study medications will then be resumed.

[figure not shown]

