Here, x_i is the treatment group indicator for participant i as in (1); Y_{i1} is the mobility score for participant i at time 1 (baseline); Y_{i2} is the mobility score for participant i at time 2 (36 month follow-up); β_0 is interpreted as the average mobility score at baseline in the reference group; β_C is interpreted as the difference in the average mobility score at baseline between the intervention group and the reference group and will be zero if the two groups are exactly comparable in their baseline values; β_L is interpreted as the average change in mobility between 36 month follow up and baseline in the reference group; β_T is interpreted as the difference average change in mobility between 36 month follow up and baseline between the intervention group and the reference group and thus the parameter of primary interest; γ_i is a random intercept for participant i that addresses the correlation in mobility across the two time points; and ε_{i1} and ε_{i2} are the residual error terms at baseline and follow-up, respectively.

This analysis will be repeated for each mobility parameter (gait speed, four stair ascent and descent time, supine to sit time), cognition scores (Trailmaking A and B, Stroop Color & Word score, and simple reaction time), and the Geriatric Depression Scale. The timed measures – Trailmaking A and B, and simple reaction time – will be inverse-transformed so that they have a speed interpretation; this will also reduce the influence of outliers. Similarly, all analyses will be repeated as stratified analyses (b - e below).

- b. Stratified according to < or > median age
- c. Stratified according to gender
- d. Stratified according to median years of education
- e. Stratified according to a clinical diagnosis of minor or major depression (for mobility and cognition)

3. Change in urinary severity index and depression category (based on the Geriatric Depression Scale) from baseline to 3 years. These analyses will be similar to the analyses for white matter hyperintensities in (1) and for mobility and cognition in (2), but using ordinal logistic regression.
 - a. According to treatment group (primary analysis)

$$\log(Y_{i1} > k / Y_{i1} \leq k) = \beta_{0k} + \beta_C x_i + \gamma_i$$

$$\log(Y_{i2} > k / Y_{i2} \leq k) = \beta_{0k} + \beta_C x_i + \beta_L + \beta_T x_i + \gamma_i$$

$$k = 1, \dots, m - 1$$

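### The achieved-BP mediator in SAP item 6 is a single month-36 ABPM session, concurrent with the outcome and without baseline adjustment, so the mediated share can be biased in either direction

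*SAP*

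**What the plan says.** SAP item 6 models change in mobility, cognition, urinary function and depressive symptoms, with change in WMH as the mediator. For the secondary versions it says that "resultant ambulatory systolic BP at 36 months regardless of treatment assignment will be considered as mediators", and gives the substitution: "Specifically, age, sex, and systolic BP will replace" the WMH-change term. Read literally, BP enters as its month-36 value, not as a change or an average over time. The equations contain treatment, time, the mediator and their interaction, with no baseline BP, age or sex as covariates.

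The outcome in the same model is also at month 36: in SAP item 2, which item 6 builds on, the second measurement "is the mobility score for participant i at time 2 (36 month follow-up"). Protocol section 5.6.4 puts both at visit 9, where patients "have final research testing for WMH, mobility, cognitive function as well as blood pressure control".

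Other ABPM data are scheduled but unused here. Section 5.5 lists ABPM at baseline and months 3, 18 and 36, and at month 6 if needed. Section 5.6 says "Follow-up ambulatory BP recordings will be made at 3 months to evaluate response to therapy". For the month-18 visit, section 5.6.3 says "ambulatory BP will be performed to evaluate achievement of therapeutic goals according to randomized treatment strategy".

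The primary regression in Protocol section 8.2 does adjust for age, sex and baseline 24-hour systolic BP.

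**The concern.** The exposure that could change function over 36 months is BP during those months. Randomisation protects the comparison of arms, but not the relation between achieved BP and outcome within arms, and the mediated share depends on that relation. Three weaknesses follow.

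- **Noise.** One session is an imperfect measure of three years of BP.
- **Confounding.** A month-36 level carries pre-randomisation BP, which may itself affect later function, and item 6 does not adjust for it.
- **Temporal order.** The mediator is recorded with the outcome, so clinical decline can alter it. Protocol section 6 allows the intensive treatment to be stopped for "intolerance to therapy (e.g. lightheadedness/syncope") or new morbidity, and invites those patients back for the month-18 and month-36 tests. SAP item 1h itself provides for patients whose BP shifts mid-trial.

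The stated primary objective is causality between 24-hour systolic BP and function. Among the planned analyses, this is the one that relates achieved 24-hour BP to functional outcomes: SAP item 1h concerns WMH and item 7d concerns adverse events. A misleading share could be read as evidence for or against BP as the mechanism.

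**Working it through.** **The plan's own figures.** The ABPM schedule, "every 15 min from 6 am to 10 pm, and every 30 min from 10 pm to 6 am", gives 16 × 4 + 8 × 2 = 80 readings, as Protocol section 5.6 states. The mediator is thus a 24-hour mean, and the noise that matters is between days and months. The documents give no reliability, power or expected share for this analysis. The nearest stated figure is 85% power for the primary gait regression (140 completers, R² rising by 0.0533 to 0.1800). It reproduces at 0.8497 with a noncentral F test, assuming two-sided 5%, and does not depend on the mediator.

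Everything below rests on assumed inputs and approximates the item 6 model by a regression of change.

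**1. Noise.** With full mediation, classical error and no interaction, the estimated share is sb² / (sb² + sw²/k). Here sb and sw are the between- and within-person SDs within an arm, and k is the number of sessions averaged.

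| sb, sw (mmHg) | k = 1 | k = 2 | k = 3 |
|---|---|---|---|
| 10, 8 | 100/164 = 61% | 100/132 = 76% | 100/121.3 = 82% |
| 7, 10 | 49/149 = 33% | 49/99 = 49% | 49/82.3 = 60% |
| 13, 6 | 169/205 = 82% | 169/187 = 90% | 169/181 = 93% |

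The comparison relevant to the fix is one session against two.

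**2. Baseline confounding.** Suppose later BP has no effect and baseline BP affects decline by 0.003 m/s per mmHg. Assume an arm difference of 12 mmHg, a total effect of 0.05 m/s, true SD 10 and within-person SD 8 at both times (observed variance 164), and a correlation of 0.3 to 0.5 between true baseline and later BP (covariance 30 to 50).

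- Unadjusted share = 0.003 × cov/164 × 12/0.05, which is 13% (cov 30) to 22% (cov 50).
- Adjusted for measured baseline BP, the slope is (0.003 × cov × 164 − 0.003 × 100 × cov) / (164² − cov²). For cov 30 this is 5.76/25,996 = 0.000222, a share of 5.3%. For cov 50 it is 9.6/24,396 = 0.000394, a share of 9.4%.

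Adjustment removes more than half of the spurious share. The rest remains because baseline BP is also measured with error.

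**3. Reverse causation.** Suppose BP has no effect and the worst 30% of decliners run 5 mmHg higher at month 36. Assume an outcome SD of 0.15 m/s, with the arm difference, total effect and SDs as in step 2. The standard normal density at the 30th percentile is 0.348.

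- Month-36 mediator: 5 × 0.348 × 0.15 / (164 + 25 × 0.21) × 12/0.05 = 37% (38% by simulation).
- Mean of two earlier sessions, neither disturbed: 0%.
- Same mean, with these patients also 2.5 to 5 mmHg higher at month 18: the mean rises by 1.25 to 2.5 mmHg. At the upper end, 2.5 × 0.348 × 0.15 / (132 + 6.25 × 0.21) × 12/0.05 = 23%; at the lower end it is 12%.

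The sign can also reverse. In a simulation with a true share of 50% and reliability 0.6, noise alone gave 0.30. A shift of 3 mmHg per SD of the outcome residual moved that to −0.11 or 0.69, depending on its direction.

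**4. Uncentred level.** The SAP's share includes INT_REF = θ_INT × α₀, and its CDE is the effect at a mediator value of zero, here 0 mmHg. Assume arm means of 143 and 130 mmHg, a PIE of 0.05 m/s, and a total effect of 0.10 m/s before any interaction.

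- θ_INT = +0.002 m/s per mmHg: INT_REF = 0.286, INT_MED = −0.026, total = 0.074. Share = (0.286 − 0.026 + 0.05)/0.074 = 4.19. Centred at 143: (−0.026 + 0.05)/0.074 = 0.32.
- θ_INT = −0.002: share = (−0.286 + 0.026 + 0.05)/0.126 = −1.67. Centred: (0.026 + 0.05)/0.126 = 0.60.

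With 140 patients, no true interaction, a true share of 50% and reliability 0.6, the 5th to 95th percentiles of the uncentred SAP share were −6.1 to 6.7. Without the interaction term they were 0.04 to 0.76.

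**The case against.** The strongest reply is that little depends on this analysis. The randomised comparison answers the causal question. The protocol's own mediation pathways are WMH and DTI, and it calls its Hypothesis 5 mediation results preliminary because the sample is too small. This stands, and it limits how much weight the point deserves.

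A second reply is that the size is assumed. This also stands: the SDs, correlation and BP shifts come from no document. Section 6 lists low-BP symptoms, new morbidity and intolerance as reasons to stop; it does not name gait or cognitive decline, and it provides for resuming medication after a temporary stop.

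A third reply is that earlier ABPM is imperfect. Titration runs for 3 to 6 months, the month-3 recording waits for stable clinic BP, month 6 is conditional, and BP after month 18 would be left out. This qualifies the fix but does not defend a mediator measured with the outcome and unadjusted for baseline BP.

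A reader might infer that the mediated share is simply understated. That needs classical error, a positive true share, no interaction and no confounding, and the documents establish none of the last three. A reader might also infer that using earlier ABPM abolishes reverse causation. Step 3 shows that this holds only if month 18 is itself undisturbed.

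**Conclusion.** The point holds as a weakness of one secondary analysis. The mediator is a single month-36 session, concurrent with the outcome, entered as a raw level and without baseline adjustment, although better-ordered data are already scheduled. The net bias in the mediated share has unknown direction.

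Under the stated assumptions, moving from one session to two raises the recovered share from 61% to 76%; the ranges, 33–82% and 49–90%, overlap widely. Adjusting for measured baseline BP cuts a spurious share of about 13–22% to about 5–10%. Entering BP uncentred makes the SAP's share hard to interpret whichever session is used.

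The documents do not support extending this to the trial's main conclusion. The primary regression, the randomised comparisons in the SAP and the sample size do not use this mediator.

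**What to change.** Amend the BP part of SAP item 6:

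- **Covariates.** Add baseline 24-hour systolic BP, with age and sex as in the primary model, to both the mediator and the outcome equations.
- **Mediator.** Define the main BP mediator from on-treatment ABPM before month 36: the month-18 recording, averaged with the last post-titration recording at month 3 or 6 where available. State the rule for patients who have both.
- **Scale.** Centre it at a value stated in advance, or express it as change from baseline, so that CDE and INT_REF have a meaning.
- **Sensitivity and status.** Report the month-36 and all-session-average versions as sensitivity analyses, and label the result exploratory.

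The cost is SAP wording, since all recordings are already scheduled. It should be settled before the database lock that the SAP places in October 2018, because choosing among BP summaries afterwards would be post hoc. Patients without a usable earlier ABPM drop out of this secondary analysis, BP after month 18 is not in the main mediator, and reverse causation is reduced but not removed.
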